### 6.3 Classification of Uncomplicated Malaria

All episodes of malaria will be classified as uncomplicated or complicated based on the following criteria:

Uncomplicated malaria (all the following must be present)

- 1) Fever ( $> 38.0^{\circ}\text{C}$  tympanic) or history of fever in the previous 24 hours
- 2) Positive thick blood smear
- 3) Absence of complicated malaria

Complicated malaria (any of the following)

- 1) Evidence of severe malaria (Appendix D) and parasitemia
- 2) Danger signs present and parasitemia
- 3) Parasite density  $> 500,000/\mu$ L

### 6.4 Management and Follow-up of Malaria

#### 6.4.1 3-day AL regimen

Following diagnosis of malaria on Study Day 0, children managed with the 3-day AL regimen will be evaluated clinically on Study Days 1, 2, 3, (4\*), 7 (8\*), 10, 14, 21, 28, 35, 42 and on any unscheduled day in which the patient is brought to the clinic (Appendix A and B). Children who do not return for a scheduled visit will be visited by a study home visitor and, if necessary, transported to the study clinic. Blood will be obtained by finger prick on Study Days 0, 1, 2, 3, (4\*), 7, (8\*), 10, 14, 21, 28, 35, 42 and on any unscheduled day in which the patient is brought to the clinic for thick blood smears (for parasite density and gametocytes) and filter paper collection (see section 6.8).

#### **6.4.2 5-day AL regimen**

Following diagnosis of malaria on Study Day 0, children managed with the 5-day AL regimen will be evaluated clinically on Study Days 1, 2, 3, 4, 5 (6\*), 7 (8\*), 10, 14, 21, 28, 35, 42 and on any unscheduled day in which the patient is brought to the clinic (Appendix A and B). Children who do not return for a scheduled visit will be visited by a study home visitor and, if necessary, transported to the study clinic. Blood will be obtained by finger prick on Study Days 0, 1, 2, 3, 4, 5 (6\*), 7, (8\*), 10, 14, 21, 28, 35, 42, and on any unscheduled day in which the patient is brought to the clinic for thick blood smears (for parasite density and gametocytes) and filter paper collection (see section 6.8).

\*participants enrolled in the intensive PK study have F/U visits on Days 4 and 8 (instead of Day 7) if receiving 3-day AL or on Days 6 and 8 if receiving 5-day AL.

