### 7.2 Artemether-lumefantrine toxicity

AL will be used to manage acute uncomplicated malaria. AL is the Ugandan first-line national regimen and would be the preferred treatment for all patients whether enrolled in this study or not. AL as a 3-day regimen is standard of care while AL as a 5-day regimen is being evaluated in this study and is a “study regimen”. Therefore, we will be assessing and recording data in relation to how participants tolerate AL. As noted in Section 1.1.8, we evaluated the impact of a cytochrome P450-inhibitor, lopinavir/ritonavir, on levels of lumefantrine in children with malaria. Day 7 levels in children on lopinavir/ritonavir-based ART had 10-fold higher day 7 levels of lumefantrine and >2-fold higher AUC, as compared to those on EFV-based ART, while exhibiting no increase in toxicity. We will, however, be recording participants tolerance of AL

using the NIH Division of AIDS Adult and Pediatric Toxicity Tables (version 2.1, March 2017; <https://rsc.tech-res.com/docs/default-source/safety/daids-ae-grading-table-mar2017.pdf>). This will be used to screen for eligibility and to evaluate adverse events for children. Study staff will receive extensive training in the identification and management of adverse events. In addition, participants will be informed by the study team about potential adverse events associated with AL and will be encouraged to present to the study clinic for all potential adverse events. Symptomatic screening for auditory AEs will be conducted at each visit. The study clinic will remain open 7 days a week so that participants may present with potential adverse events as they arise. Monitoring, reporting, and management of adverse events is described below, and will follow guidelines set forth by each respective institution.

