## 8.0 MONITORING OF ADVERSE EVENTS AND MANAGEMENT

An adverse event is defined as "unfavorable changes in health, including abnormal laboratory findings that occur in study participants during the study or within a specified period following the study". There are no "study drugs" in this study, and all therapies being studied for PK are the standard of care in Uganda and provided free of charge by the Ministry of Health outside of study participation. This study will be directly observing administration of AL (Coartem®) to participants for the treatment of malaria. Data regarding the tolerance of AL will be recorded. Study clinicians will assess patients at each scheduled and unscheduled visit to the clinic according to a standardized clinical record form using scales developed by the NIH Division of AIDS Adult and Pediatric Toxicity Tables version 2.1, March 2017. Guidelines for reporting of adverse events due to study participation provided by UCSF Human Research Protection Program and Institutional Review Board, Yale Human Investigations Committee, NICHD, Makerere University School of Medicine Research Ethics Committee (SOMREC), and the Ugandan National Council for Science and Technology will be followed as described below.

Per UCSF HRPP & IRB guidelines as found on website updated April, 2017: Adverse events which are definitely, probably, or possibly related to study procedures or study participation **AND** serious or unexpected will be reported. AEs which do not meet those criteria will be documented, referenced, and retained in the study files for follow-up. Per UCSF HRPP & IRB guidelines, the following definitions for serious or unexpected adverse events will be followed:

\*Serious Adverse Event (SAE) is any AE that results in any of the following outcomes:

- Death,
- Life-threatening adverse experience,
- Inpatient hospitalization or prolongation of existing hospitalization,
- Persistent or significant disability/incapacity,
- Congenital anomaly/birth defect, or cancer, or
- Any other experience that suggests a significant hazard, contraindication, side effect or precaution that may require medical or surgical intervention to prevent one of the outcomes listed above,
- Event occurring in a gene therapy study
- Event that changes the risk/benefit ratio of the study.

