#### 9.2.2 Secondary outcomes

- 1) Safety of 5-day vs 3-day AL regimens
- 2) Prevalence of gametocytemia following treatment in 3-day vs 5-day AL regimens
- 3) Weight-for-age and Height-for-age associations with PK
- 4) Diagnostic sensitivity of LAMP, HS-RDT, and microscopy for the detection of recurrent parasitemia.
- 5) Metabolomic measurements in HIV infected vs HIV uninfected children
- 6) Relationship between molecular markers of drug resistance and treatment failure

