### Explanation of Intensive PK schedule of events (Appendix A):

- 1 As is standard practice, study Day 0 stipulates the time of diagnosis of uncomplicated malaria and initiation of AL treatment.
- 2 Rapid HIV test will be performed to determine eligibility to enroll as either HIV infected or HIV uninfected participant, although children must be stabilized on EFV-based ART for 10 days prior to enrollment. Positive HIV test results to be confirmed by Western Blot or HIV RNA after enrollment.
- 3 History will include general medical history, diagnosis, medication (including ingestion of herbs), allergies, and current symptoms.
- 4 Physical examination will include weight, height, and vital signs (temperature, pulse, blood pressure, respiratory rate), lymphadenopathy, hepatomegaly, splenomegaly, infections in ears, mouth, pharynx or skin and pulmonary, cardiac, neurologic or skeletal abnormalities and anthropometric assessments. Mid-upper arm circumference will also be collected at time of first enrollment for each episode of malaria.
- 5 Hematology/chemistry draws entail a 4mL venous sample for CBC, differential, ALT/AST, and creatinine. AST is incorporated as part of chemistries at all blood draws.
- 6 A thin smear is performed to assist in species identification.
- 7 Dosing of AL for all subjects undergoing intensive PK sampling will be scheduled to assure the last dose of a six or 10 dose regimen is given in the morning (Day 3 or 5).
- 8 On stable ART as per clinical management in TDH or MGH or other referral clinic; ART dosing permitted at home, but time of administration is recorded
- 9 For subjects participating in intensive PK evaluations, sampling for the 120 PK sample will occur on Day 8 since these subjects receive the 6th or 10th AL dose on Day 3 or 5.
- 10 Patients presenting on an unscheduled day for a sick visit will undergo sampling for lumefantrine PK if found to have a positive malaria thick
- 11 Specifically, for children receiving 5-day AL
- 12 At 2 and 8 hours an additional 200µL will be drawn via a capillary stick to permit correlation of venous and capillary concentrations for the artemisinins.
- 13 At approximately 0, 24, 48, and 72, 84 and 96 hours post the first dose of AL or until blood smears are consistently negative. In a subset of participants, additional thick blood smears will be done on the days of AL doses to assess parasite clearance.

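### Two extra early visits in the 5-day arm, with a history limited to current symptoms, can record more transient events on 5-day AL at equal true rates

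*Combined protocol and SAP*

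**What the plan says.** Section 6.4.1: "children managed with the 3-day AL regimen will be evaluated clinically on Study Days 1, 2, 3", then on Day 7 in the population study. A note under Section 6.4.2 adds that "participants enrolled in the intensive PK study have F/U visits on Days 4 and 8 (instead of Day 7) if receiving 3-day AL".

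Section 6.4.2: "children managed with the 5-day AL regimen will be evaluated clinically on Study Days 1, 2, 3, 4, 5", then Day 7 in the population study, or Days 6 and 8 in the intensive study.

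Appendix A agrees for the intensive study. Its Day 5 and Day 6 history and examination carry footnote 11: "Specifically, for children receiving 5-day AL". Appendix B, for the population study, marks history and examination on Days 4 and 5 without that footnote, although the dosing and PK sampling rows of the same table carry it.

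On harms, Section 8.0 says that "Study clinicians will assess patients at each scheduled and unscheduled visit to the clinic", and Section 7.2 says that "Symptomatic screening for auditory AEs will be conducted at each visit". Footnote 3 of both appendices ends the content of the history with "allergies, and current symptoms". Section 9.2.2 lists "Safety of 5-day vs 3-day AL regimens" as the first secondary outcome. Section 9 gives no event window, denominator or test for it, and no allowance for unequal visits.

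**The concern.** How often harms are looked for depends on the randomised regimen. A child in either arm may have a day of vomiting, headache or dizziness between Days 4 and 6. On 5-day AL a scheduled visit is likely to find it. On 3-day AL it may have resolved by Day 7 or 8, where the history does not explicitly ask about resolved symptoms. Any resulting bias runs towards more events on 5-day AL. It would be mixed with any real effect of the four added doses (10 v 6), which is what the first secondary objective sets out to assess.

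**Working it through.** The documents give no adverse event rate, safety power or safety sample size, so there is no figure to reproduce.

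**Visit counts after Day 0 (Sections 6.4.1 and 6.4.2)**

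| | 3-day | 5-day |
|---|---|---|
| Population | 1, 2, 3, 7, 10, 14, 21, 28, 35, 42 = 10 | adds 4, 5 = 12 |
| Intensive | 1, 2, 3, 4, 8, 10, 14, 21, 28, 35, 42 = 11 | adds 5, 6 = 13 |

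Section 6.4 counts Day 10 as a clinical evaluation, but the appendices show no history or examination that day. The difference is two visits either way. If Appendix B is read literally, the population difference is zero. The imbalance then affects only the intensive study: 160 of 380 children, a mean of 2 × 160/380 = 0.84 extra visits.

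**Illustrative detection model (assumptions, not document figures).** True rates are equal, onset is uniform over Days 0-7, and duration is exponential with mean m days. An event is found if it is still present at the next visit. If it has resolved, it is recalled with probability r. With no recall, the proportion detected is

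D = (m/7) × Σ(1 − e^(−gap/m)), summed over the gaps between visits.

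Population gaps to Day 7 are 1, 1, 1, 4 (3-day) and 1, 1, 1, 1, 1, 2 (5-day).

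- m = 0.5: D = 0.257 v 0.379, ratio 1.48.
- m = 1: D = (3 × 0.632 + 0.982)/7 = 0.411 v (5 × 0.632 + 0.865)/7 = 0.575, ratio 1.40.
- m = 2: D = 0.584 v 0.743, ratio 1.27.
- m = 7: ratio 1.10.

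The intensive schedule gives the same values. As a simple check, events lasting exactly one day are caught for 4 of 7 onset days v 6 of 7, a ratio of 1.5.

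**Recall.** Detection becomes r + (1 − r)D. For m = 1 and r = 0.5 this is 0.706 v 0.788, ratio 1.12.

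| Recall | Ratio, onset Days 0-7 (m = 0.5 to 7) | Ratio, onset Days 0-42 (m = 0.5 to 7) |
|---|---|---|
| 0% | 1.10-1.48 | 1.02-1.18 |
| 50% | 1.04-1.12 | 1.01-1.02 |
| 90% | at most 1.02 | about 1.00 |
| 100% | 1.00 | 1.00 |

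**If Appendix B governs the population study.** Each regimen has 80 intensive and 110 population children. For m = 1 the 3-day arm detects (80 × 0.411 + 110 × 0.575)/190 = 0.506 v 0.575, ratio 1.14 with no recall. For m = 0.5 and m = 2 the same sum gives 1.16 and 1.10.

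**Chance of a false significant excess on 5-day AL.** This uses Section 6.4 visits, 190 children per regimen (80 + 110, the maximum, one episode each) and an assumed 30% true incidence. The formula is Φ((p5 − p3)/SE − 1.96), with SE = √[(p3(1 − p3) + p5(1 − p5))/190].

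- Days 0-7, m = 1, no recall: p3 = 0.123, p5 = 0.173, SE = 0.036, chance 27%.
- Days 0-7, m = 2: 21% with no recall, 8% with 50% recall, 3% with 90% recall.
- Days 0-42, m = 1 to 2, no recall: 4-5%.

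The nominal figure is 2.5%.

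**The case against.** - **Recall and self-presentation.** Both arms attend Day 7/8, and footnote 3 also lists general medical history. Section 7.2 encourages families to come in for any potential adverse event, and the clinic is open every day. This stands as a limit on size: with 90% recall the ratio is at most 1.02. But the plan does not fix the recall period, so how far this protects the comparison is left to practice.
- **Mild events get no report form.** Section 7.3 reserves the form for events of grade 3 or higher that are also serious or unexpected. However, Section 8.0 has clinicians grade patients on a standard record at each visit and keeps non-reportable events in the study files. The plan does not say which of these records feed the safety comparison.
- **Other safety data are balanced.** Laboratory tests fall on Days 0, 14 and 28 in both arms, and the number of ECGs per child is the same in each regimen. This stands: the issue is confined to transient clinical symptoms.
- **The extra visits follow exposure.** Each arm is seen through the day after its last dose, and morning doses are observed in clinic, so the visits are needed. That justifies holding them. It does not make a comparison counted from Day 0 even.

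A reader might infer that the trial will report a false excess, or that an excess could not be told apart from a real effect. The documents support neither. The bias vanishes with full recall, and the visit day of each finding would allow events to be separated. A reader might also infer that the main comparison should be limited to days both arms share. That would remove the window of the added doses, including the Day 5 ECGs around the last dose in the intensive study, and could hide real harm.

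**Conclusion.** The point holds as a possible, bounded ascertainment bias. In the intensive study the 5-day arm has two more clinical evaluations under both Section 6.4 and Appendix A. In the population study Section 6.4 gives the same difference, while Appendix B shows none. That conflict covers up to 220 of 380 children.

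For brief clinical events arising in Days 0-7, the detected ratio at equal true rates runs from 1.00 to roughly 1.3-1.5. Over 42 days it is close to 1 unless events are very short and never recalled. Serious events are little affected. The rate, duration, onset pattern and recall behind these figures are all assumed, so they give a range and not a forecast. The case for acting rests on the low cost of the remedy more than on a demonstrated distortion.

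**What to change.** 1. In footnote 3 of Appendices A and B, replace the item on current symptoms with *all symptoms since the previous visit, with onset and stop dates*. At Day 7/8, ask both arms about symptoms since the last visit day they share: Day 3 in the population study and Day 4 in the intensive study, or the later shared day if item 2 changes it.
2. Reconcile Section 6.4.1 with Appendix B on whether 3-day population children have history and examination on Days 4 and 5.
3. In Section 9, keep all events in the main 5-day v 3-day safety comparison. Add one sensitivity analysis that flags events found solely at the extra 5-day visits.

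The cost is a change to the footnote and case report form, one corrected schedule entry and a sentence in the analysis section. Items 1 and 3 need no new visits. The downside is reliance on caregiver recall over up to four days (Day 3 to 7, or Day 4 to 8).

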#### **6.4.3 Timing of doses**

The time of AL and EFV administration will be noted whether at home or in the clinic. It is critical for PK studies that the time of AL and EFV administration and the time of all PK sample collections be recorded on the Case Report Forms.

All PK samples will be immediately placed on dry ice, processed for plasma separation, transferred to liquid nitrogen, and shipped at a later date on dry ice to our laboratory in San Francisco for analysis.

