### **3.2.3 All children**

- If a child has multiple episodes of malaria, they will be randomized for each episode into a 3-day or 5-day regimen. For example, a child could be randomized to a 3-day regimen for episode #1 and then randomized to either a 3-day or 5-day regimen for episode #2, or vice-versa.
- All sample sizes refer to “evaluable” PK participants, in other words, those that have completed follow-up sufficiently to obtain all required PK study samples (see Note\*).
- If a child does not complete PK sampling procedures for the intensive study for any reason (they are not “evaluable”), the child may be re-enrolled in the intensive PK study for subsequent episode(s) of malaria, if they meet eligibility requirements.
- All children can be enrolled into the intensive study for a maximum of two “evaluable” episodes of malaria.
  - \*Note: Up to 2 PK samples can be missing to still be considered “evaluable” for intensive PK. More than 2 missing PK samples will permit a child to either repeat a specific intensive study for a subsequent episode or be replaced. They may also be eligible to transition from the intensive study into the population PK sampling study, provided enrolment criteria are met. For any malaria episodes beyond the 4th episode, a child will be referred to the local health center for management.
- At least 28 days must separate each PK study malaria episode.
- All children will preferentially undergo intensive PK studies until the maximum of two episodes in the intensive sampling scheme has been reached

- A child may be enrolled for a maximum of 4 episodes of malaria over the study period whether deemed “evaluable” or not. For any malaria episodes beyond the 4th episode, a child will be referred to the local health center for management.
- If participation in the intensive study is not feasible for any reason or if the desired intensive sampling size has not been achieved, a child can be directly enrolled into the population studies.

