### **Sampling for artemether, dihydroartemisinin and lumefantrine.**

*Capillary* samples (200 µL each\*) will be collected by finger stick at approximately 2 and 4 hours post- each morning AL dose. A pre-1st dose sample will also be collected to confirm no residual antimalarial drug is detectable. On Study Day 1 (when a single dose is administered mid-day) capillary samples will also be collected at approximately 2 and 4 hours post- this dose.

Intensive *venous* sampling will occur via an indwelling catheter prior to and 0.5 1, 2, 3, 4, 6 and 8 hours post-administration of the 6th or 10th dose (for the 3-day and 5-day AL regimens, respectively) for the determination of artemether, DHA, and lumefantrine concentrations in plasma (500 µL each\*). Participants will remain in the clinic until completion of the 8-hour blood sampling on Study Day 3 or 5 (for the 3-day and 5-day AL regimens, respectively) and discharged home. They will then return to the clinic the next morning for the 24-hour sample.

To determine the correlation between capillary and venous artemisinin exposure, a simultaneous capillary sample (200 µL) will be collected at the time of the 2 and 8-hour samples.

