### **6.7.3 PK Sample collection and handling**

For consistency, blood samples will be obtained from capillary or venous sources, as specified. However, if venous PK samples cannot be obtained at desired times due to technical or other limitations, technicians may obtain blood from a capillary site. Prior correlation studies between venous and capillary measurements for lumefantrine have confirmed the ratio of concentrations is 1:1. For the artemisininis, correlation studies will be carried out in the context of this protocol.

All samples will be immediately placed on dry ice, processed for plasma, transferred to liquid nitrogen, and shipped at a later date on dry ice to our laboratory for analysis. Liquid nitrogen will be obtained from Kampala.

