### **6.7.4 Assays for artemether, DHA and lumefantrine**

Artemether, DHA and lumefantrine and active desbutyl-lumefantrine will be measured using optimized methods validated in our laboratory. All methods will utilize liquid chromatography tandem mass spectrometry.

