**Molecular studies.** Parasite genotyping using polymorphic markers will be conducted to assess genetic diversity using methods routine in our laboratory to determine the multiplicity of infection (MOI). Six polymorphic markers (merozoite surface protein (MSP)-1, MSP-2, and 4 microsatellites) will be typed using capillary electrophoresis. For drug resistance genotyping, extracted DNA will be amplified by PCR, and following amplification, multiplex LDR will be conducted with bead-specific oligonucleotides, followed by hybridization to magnetic beads, and fluorometric assessment of mutation prevalence on a Bio-Plex system (Bio-Rad, Hercules, CA). RNA-based studies will also be performed for more sensitive detection of asexual blood stages and gametocytes. RNA-based studies will allow for the most sensitive quantification of parasite and gametocyte clearance between study regimens, as well as early detection of recurrent parasitemia.

**Metabolomics studies.** Metabolomics assays will be conducted using plasma and/or RBC pellets. 20 $\mu$ L of plasma will be placed in an ice-cold methanol solution, vortexed, and stored in -80°C. De-identified metabolomics study samples will be shipped on dry ice to the lab of [name], an expert in malaria metabolomics, at Monash University for analysis.

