### 9.2 Outcome Measures

#### 9.2.1 Primary outcomes

- 1) Area under the plasma concentration versus time curve for all drug analytes.
- 2) Recurrent malaria following treatment by day 42 (recrudescence or new infection)

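### Sections 6.4.3 and 6.7.3 put every PK sample on dry ice before plasma is separated; followed literally, this would leave no valid plasma for the primary AUC, and both sentences need correcting

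*Combined protocol and SAP*

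**What the plan says.** The protocol gives the handling order for PK samples twice. Section 6.4.3 (Timing of doses): "All PK samples will be immediately placed on dry ice, processed for plasma separation, transferred to liquid nitrogen". Section 6.7.3 (PK Sample collection and handling): "All samples will be immediately placed on dry ice, processed for plasma, transferred to liquid nitrogen, and shipped at a later date on dry ice". In both, dry ice comes first and at once, plasma processing second, liquid nitrogen third and shipment last.

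The quantity to be measured is a plasma concentration. The first primary outcome in section 9.2.1 is "Area under the plasma concentration versus time curve for all drug analytes". Section 6.7.1 describes the intensive venous samples as being "for the determination of artemether, DHA, and lumefantrine concentrations in plasma". The population model in section 9.5.2 also works on plasma concentrations. Section 6.7.4 says that the analytes "will be measured using optimized methods validated in our laboratory" and mentions no whole-blood or haemolysed matrix.

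**The concern.** Plasma has to be separated from blood that is still liquid and whose cells are intact. A rule that sends fresh whole blood straight to dry ice reverses that order. The thawed tube would hold a lysate of plasma and red cell contents, and centrifuging it would not give the plasma back. Any concentration measured in it would be a different quantity from the one named as the primary outcome.

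The step cannot be undone for a sample once it is frozen. The instruction also reaches every arm and both study components, because it is written for all PK samples without exception. Two clinics, Tororo and Masafu (section 3.3), would be working from the same text.

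**Working it through.** No sample size, power or alpha figure is involved. The check sets the passages side by side, counts the samples affected, and then asks whether a bias can be computed.

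**1. Is the order really freeze first?** Both sentences are lists of steps, and the later steps are plainly in time order (liquid nitrogen, then shipment at a later date). Shipping on dry ice has its own mention at the end, so the first mention of dry ice cannot be the shipping step. No other section gives a different step before separation, a temperature before centrifugation or a time limit to centrifugation. The documents cite no laboratory manual that would override the order.

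**2. Would the blood freeze?** The volumes are 200 µL capillary and 500 µL venous (section 6.7.1). Dry ice is at about -78 °C, and red cells that are frozen and thawed rupture. This is general physical fact; the documents do not state it. They give no time on dry ice, so a very brief contact is not excluded, but immediate placement of such small volumes makes freezing the natural reading.

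**3. How many samples are covered?** From Appendix A and section 6.7.1, per intensive episode:

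- 3-day regimen: day 0, 3; day 1, 2; day 2, 2; day 3, 8 venous + 2 paired capillary = 10; days 4, 8, 14 and 21, 1 each = 4. Total 3 + 2 + 2 + 10 + 4 = 21.
- 5-day regimen: day 0, 3; days 1 to 4, 2 each = 8; day 5, 8 venous; days 6, 8, 14 and 21, 1 each = 4. Total 3 + 8 + 8 + 4 = 23. Section 6.7.1 also describes paired capillary samples at 2 and 8 hours, which Appendix A shows only for the 3-day regimen; with them the total is 25.

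Section 3.2.3 says: "Up to 2 PK samples can be missing to still be considered" evaluable. If a sample frozen before separation counted as missing, the literal rule would leave no intensive episode evaluable.

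**4. Can a bias be computed?** For a full lysate, concentration relative to plasma = (1 - Hct) + Hct × Kp, where Hct is the hematocrit and Kp the red cell to plasma concentration ratio. If Kp = 1, the ratio is 1 at any hematocrit and nothing changes. If Kp is below 1 the result is too low; if above 1, too high. The documents give no Kp for artemether, DHA, lumefantrine or desbutyl-lumefantrine, and no hematocrit by HIV group or by study day. Neither the sign nor the size follows.

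**The case against.** The strongest reply is that this is a slip of wording. Both sentences say that the sample is processed for plasma, and sections 6.7.1, 9.2.1 and 9.5.2 all require plasma. A laboratory that froze first could not deliver it, so the intended result is clear. The team also reports earlier intensive PK studies of the same drug (section 5.1.1) and validated assays. The two sentences are nearly identical, so the second looks copied and does not independently confirm a deliberate rule. All of that stands, and it is why practice may well be sound. It does not remove the point: the text is an operative instruction, it is the only one given, and staff who handled samples correctly would be departing from it.

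A second reply is that the 3-day versus 5-day comparison is randomised within each HIV group, and that hematocrit is a planned covariate in the population model (section 9.5.2). This also stands in part. Randomisation limits systematic distortion of that comparison. The HIV-infected versus HIV-uninfected comparison is not randomised, and the intensive analysis in section 9.4.2 (t-test or ANOVA) does not adjust for hematocrit.

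A reader might extend the point to metabolomics, since section 6.8 says: "Metabolomics assays will be conducted using plasma and/or RBC pellets". The documents do not support that. Appendix A lists blood for metabolomics and molecular studies as a separate collection, section 6.8 gives metabolomics its own handling, and the two dry ice sentences concern PK samples.

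**Conclusion.** The point holds as a defect in the written instruction. Followed literally, sections 6.4.3 and 6.7.3 would prevent valid measurement of the plasma concentrations behind the first primary outcome, for every PK sample in the study. This rests on two assumptions: that the listed steps are carried out in the listed order, and that contact with dry ice lasts long enough to freeze 200 to 500 µL of blood. The likeliest explanation is a wording error repeated in both places. The documents do not show that any sample was or will be mishandled.

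Stronger readings are tempting and should not be drawn. A reader might choose a value for Kp, take two individual hematocrits (section 4.2 admits hemoglobin down to 7.0 g/dL) and set the resulting percentage beside the 35% AUC difference in section 9.4.1. Kp would be a guess, and a contrast between two individuals is not a difference between group means, so the comparison has no footing. Nor do the documents show that hematocrit differs between the HIV groups, so a bias in that contrast is possible but not established. They contain nothing on chemical loss of the artemisinins in lysed blood. Section 9.4.1 draws its AUC and CV assumptions from the team's studies and the literature without naming Table 1, so a mismatch with Table 1 cannot be argued either. The sample size and analysis plan are not affected by this point.

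**What to change.** Correct sections 6.4.3 and 6.7.3 together, so that neither keeps the present order:

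- Whole blood is kept chilled but not frozen until centrifugation.
- Plasma is separated within a stated maximum time, and the actual time is recorded. The laboratory should set the limit from its own validation data.
- Only the separated plasma goes into liquid nitrogen and is later shipped on dry ice.
- Any sample frozen before separation is recorded and flagged, and a sensitivity analysis of the AUC omits flagged samples.

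Flagging is enough. An automatic exclusion would go further than needed and, if the literal order had been followed throughout, would remove every PK sample. If samples have already been taken, both sites should document what was done.

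The cost is a revised sentence in each of two sections, a time and a flag to record for each sample, and one added sensitivity analysis. No extra samples or participants are needed.
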